
Immune-related meningoencephalitis is an identified risk associated with the administration of atezolizumab. Immune-related meningoencephalitis should be suspected in any patient presenting with signs or symptoms suggestive of meningitis or encephalitis, including, but not limited to, headache, neck pain, confusion, seizure, motor or sensory dysfunction, and altered or depressed level of consciousness.

Encephalopathy from metabolic or electrolyte imbalances needs to be distinguished from potential meningoencephalitis resulting from infection (bacterial, viral, or fungal) or progression of malignancy, or secondary to a paraneoplastic process.

All patients being considered for meningoencephalitis should be urgently evaluated with a CT scan and/or MRI scan of the brain to evaluate for metastasis, inflammation, or edema. If deemed safe by the treating physician, a lumbar puncture should be performed and a neurologist should be consulted.

Patients with signs and symptoms of meningoencephalitis, in the absence of an identified alternate etiology, should be treated according to the guidelines in [Table 11](#).

Table 11 Management Guidelines for Immune-Related Meningoencephalitis

Event	Management
Immune-related meningoencephalitis, all grades	
 • Permanently discontinue atezolizumab and contact Medical Monitor.^a • Refer patient to neurologist. • Initiate treatment with 1–2 mg/kg/day IV methylprednisolone or equivalent and convert to 1–2 mg/kg/day oral prednisone or equivalent upon improvement. • If event does not improve within 48 hours after initiating corticosteroids, consider adding an immunosuppressive agent. • If event resolves to Grade 1 or better, taper corticosteroids over ≥ 1 month.

^a Resumption of atezolizumab may be considered in patients who are deriving benefit and have fully recovered from the immune-related event. Patients can be re-challenged with atezolizumab only after approval has been documented by both the investigator (or an appropriate delegate) and the Medical Monitor.

Appendix 8 Risks Associated with Atezolizumab and Guidelines for Management of Adverse Events Associated with Atezolizumab (cont.)

RENAL EVENTS

Immune-related nephritis has been associated with the administration of atezolizumab. Eligible patients must have adequate renal function, and renal function, including serum creatinine, should be monitored throughout study treatment. Patients with abnormal renal function should be evaluated and treated for other more common etiologies (including prerenal and postrenal causes, and concomitant medications such as non-steroidal anti-inflammatory drugs). Refer the patient to a renal specialist if clinically indicated. A renal biopsy may be required to enable a definitive diagnosis and appropriate treatment.

Patients with signs and symptoms of nephritis, in the absence of an identified alternate etiology, should be treated according to the guidelines in [Table 12](#).

Appendix 8

Risks Associated with Atezolizumab and Guidelines for Management of Adverse Events Associated with Atezolizumab (cont.)

Table 12 Management Guidelines for Renal Events

Event	Management
Renal event, Grade 1	
 • Continue atezolizumab. • Monitor kidney function, including creatinine, closely until values resolve to within normal limits or to baseline values.
Renal event, Grade 2	
 • Withhold atezolizumab for up to 12 weeks after event onset. ^a • Refer patient to renal specialist. • Initiate treatment with corticosteroids equivalent to 1–2 mg/kg/day oral prednisone. • If event resolves to Grade 1 or better, resume atezolizumab. ^b • If event does not resolve to Grade 1 or better while withholding atezolizumab, permanently discontinue atezolizumab and contact Medical Monitor. ^c
Renal event, Grade 3 or 4	
 • Permanently discontinue atezolizumab and contact Medical Monitor. • Refer patient to renal specialist and consider renal biopsy. • Initiate treatment with corticosteroids equivalent to 1–2 mg/kg/day oral prednisone. • If event does not improve within 48 hours after initiating corticosteroids, consider adding an immunosuppressive agent. • If event resolves to Grade 1 or better, taper corticosteroids over ≥1 month.

^a Atezolizumab may be withheld for a longer period of time (i.e., >12 weeks after event onset) to allow for corticosteroids (if initiated) to be reduced to the equivalent of ≤10 mg/day oral prednisone. The acceptable length of the extended period of time must be agreed upon by the investigator and the Medical Monitor.

^b If corticosteroids have been initiated, they must be tapered over ≥1 month to the equivalent of ≤10 mg/day oral prednisone before atezolizumab can be resumed.

^c Resumption of atezolizumab may be considered in patients who are deriving benefit and have fully recovered from the immune-related event. Patients can be re-challenged with atezolizumab only after approval has been documented by both the investigator (or an appropriate delegate) and the Medical Monitor.

SYSTEMIC IMMUNE ACTIVATION

Systemic immune activation is a rare condition characterized by an excessive immune response. Given the mechanism of action of atezolizumab, systemic immune activation is considered a potential risk when atezolizumab is given in combination with other immunomodulating agents.

Appendix 8

Risks Associated with Atezolizumab and Guidelines for Management of Adverse Events Associated with Atezolizumab (cont.)

Recommendations regarding early identification and management of systemic immune activation are provided below. In the event of suspected systemic immune activation, atezolizumab should be withheld and clinical specialists (e.g., rheumatology, clinical immunology, or solid organ or hematopoietic stem cell transplant specialists) and the Medical Monitor should be consulted for additional guidance.

Early disease recognition is critical, and systemic immune activation should be suspected if, in the absence of an alternative etiology, the patient meets two or more of the following criteria:

- Hypotension that is refractory to aggressive IV fluid challenge
 Vasopressor support may be required.
- Respiratory distress that requires aggressive supportive care
 Supplemental oxygen and intubation may be required.
- Fever > 38.5°C
- Acute renal or hepatic failure
- Bleeding from coagulopathy
- Any of the following unexplained laboratory abnormalities (change from baseline):
 cytopenias (in two or more lineages), significant transaminitis, or coagulopathy

For patients with suspected systemic immune activation, an initial evaluation should include the following:

- CBC with peripheral smear
- PT, PTT, fibrinogen, and D-dimer
- Ferritin
- Soluble interleukin 2 (IL-2) receptor (soluble CD25)
- Triglycerides
- AST, ALT, and direct bilirubin
- LDH
- Complete neurologic and abdominal examination (assess for hepatosplenomegaly)

Laboratory tests with normal results should be repeated frequently in patients for whom a high clinical suspicion of systemic immune activation exists.

If neurologic abnormalities are present, consider cerebrospinal fluid analysis and/or an MRI of the brain.

Appendix 8

Risks Associated with Atezolizumab and Guidelines for Management of Adverse Events Associated with Atezolizumab (cont.)

If cytopenias are present (Grade ≥ 2 in two or more lineages) or ferritin is ≥ 3000 ng/mL, the following evaluations should also be performed:

- Bone marrow biopsy and aspirate (assess for evidence of hemophagocytosis)
- Adenovirus, cytomegalovirus, Epstein-Barr virus, herpes-simplex virus, and human herpesvirus 6, 7, and 8 evaluation (for reactivated or active disease)

Diagnostic criteria and recommended management for systemic immune activation are provided in [Table 13](#). The diagnostic criteria apply only when alternative etiologies have been excluded.

An adverse event of systemic immune activation should be reported on the Adverse Event eCRF if it meets the criteria for "consistent with systemic immune activation" or "probable systemic immune activation" as outlined in [Table 13](#).

Appendix 8

Risks Associated with Atezolizumab and Guidelines for Management of Adverse Events Associated with Atezolizumab (cont.)

Table 13 Diagnostic Criteria and Recommended Management for Systemic Immune Activation

Systemic Immune Activation Diagnostic Criteria (applicable only when alternative etiologies have been excluded)		
Major Criteria		Minor Criteria

 • Fever $\geq 38.5^{\circ}\text{C}$ on more than one occasion • Ferritin ≥ 3000 ng/mL • Cytopenias (Grade ≥ 2 in two or more lineages) • Age-adjusted soluble interleukin-2 receptor elevated by ≥ 2 standard deviations • Severe (Grade ≥ 3) or progressive dysfunction in two or more organs • Decreased fibrinogen 		
 • Splenomegaly • Hemophagocytosis in bone marrow, spleen, or lymph nodes • Elevated γ-glutamyl transpeptidase (GGT) or liver function tests (AST, ALT, or direct bilirubin) • Elevated triglycerides • Elevated LDH • Decreased natural killer cell activity
Diagnosis and Management of Systemic Immune Activation		
Number of Criteria	Diagnosis	Action to Be Taken
≥ 4 major criteria	Consistent with systemic immune activation	
 • Permanently discontinue atezolizumab. • Consider treatment with an immunosuppressive agent (i.e., cytokine inhibitors) and IV corticosteroids (i.e., methylprednisolone 1 g once daily or equivalent, or dexamethasone ≥ 10 mg/m² once daily if neurologic abnormalities are present). • Contact the Medical Monitor for additional recommendations. • Consider HLH-2004 protocol if there is no clinical improvement.
3 major criteria OR 2 major plus ≥ 3 minor criteria	Probable systemic immune activation	
 • Depending on clinical severity, follow guidelines for “Consistent with systemic immune activation” or “Possible systemic immune activation” diagnosis. • Clinical specialists and the Medical Monitor may be contacted for recommendations.
2 major plus ≤ 2 minor criteria OR 1 major plus ≥ 4 minor criteria	Possible systemic immune activation	
 • Withhold atezolizumab. • Consider treatment with IV corticosteroids. • Clinical specialists and the Medical Monitor may be contacted for additional recommendations. • Follow guidelines for “Consistent with systemic immune activation” diagnosis if there is no clinical improvement or if clinical worsening occurs. • If clinical improvement occurs, atezolizumab may be resumed following a benefit-risk assessment by the Medical Monitor.

Notes: Criteria are adapted from a Delphi Survey of 26 experts who provided helpful criteria in the positive diagnosis of hemophagocytic syndrome in adult patients (Hejblum et al. 2014).

Grades are based on National Cancer Institute Common Terminology Criteria for Adverse Events.

These recommendations do not replace clinical judgment and are intended as suggested guidance.

Appendix 8
Risks Associated with Atezolizumab and Guidelines for
Management of Adverse Events Associated with Atezolizumab
(cont.)

REFERENCES

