5.1.3.3 Management of Cobimetinib- and Atezolizumab-Specific Adverse Events

Toxicities associated or possibly associated with cobimetinib plus atezolizumab treatment should be managed according to standard medical practice. See [Appendix 8](#) for management of adverse events related to atezolizumab.

For management of cobimetinib- and atezolizumab-specific toxicities, including IRRs, gastrointestinal toxicity, dermatologic toxicity, hepatotoxicity, pulmonary toxicity, potential eye toxicity, reductions in LVEF from baseline, rhabdomyolysis, elevated CPK, and hemorrhage, see [Table 6](#).

Table 6 Guidelines for Management of Patients Who Experience Specific Adverse Events (Cobimetinib and Atezolizumab)

Event	Action to Be Taken

General guidance for dose modifications and treatment delays and discontinuation
	
 • There will be no dose modifications for atezolizumab. • If atezolizumab is withheld and corticosteroids are initiated for an atezolizumab-related toxicity, corticosteroids must be tapered over ≥ 1 month to ≤ 10 mg/day oral prednisone or equivalent before atezolizumab can be resumed.^{a, b, c} 
The dose of cobimetinib can be reduced by 20 mg (one dose level) up to two times (i.e., from 60 mg to 40 mg and then from 40 mg to 20 mg). If further dose reduction is indicated after two dose reductions, the patient must discontinue cobimetinib but may continue treatment with atezolizumab at the investigator's discretion.
 
 • If atezolizumab is discontinued, treatment with cobimetinib may be continued at the investigator's discretion and after discussion with the Medical Monitor. • If cobimetinib is withheld for > 28 days because of toxicity, the patient should be discontinued from cobimetinib, unless resumption of treatment is approved by the Medical Monitor after discussion with the investigator. • If atezolizumab is withheld for > 105 days because of toxicity, the patient should be discontinued from atezolizumab, unless resumption of treatment is approved by the Medical Monitor after discussion with the investigator.

IRRs, anaphylaxis, and hypersensitivity reaction
	
 • Guidelines for management of IRRs are provided in Appendix 8. • For anaphylaxis precautions, see Appendix 7. • For severe hypersensitivity reactions, permanently discontinue all study treatment.

IRR=infusion-related reaction.

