Colitis, Grade 2	
 • Withhold atezolizumab and cobimetinib. • Initiate supportive care and monitor patient closely. • Discontinue medications that may exacerbate colitis (e.g., NSAIDs). • Refer patient to GI specialist for evaluation and confirmatory biopsy. • For recurrent events or events that persist > 5 days, initiate treatment with 1–2 mg/kg/day oral prednisone or equivalent. • If event resolves to Grade 1 or better within 105 days, resume atezolizumab at fixed dose. If not, permanently discontinue atezolizumab and cobimetinib.^{a, b, c} • If event resolves to Grade 1 or better within 28 days, resume cobimetinib with dose reduced by one level. If not, permanently discontinue cobimetinib.
Colitis, Grade 3	
 • Withhold atezolizumab and cobimetinib. • Initiate supportive care and monitor patient closely. • Discontinue medications that may exacerbate colitis (e.g., NSAIDs). • Refer patient to GI specialist for evaluation and confirmatory biopsy. • Initiate treatment with 1–2 mg/kg/day IV methylprednisolone or equivalent and convert to 1–2 mg/kg/day oral prednisone or equivalent upon improvement. • If event resolves to Grade 1 or better within 105 days, resume atezolizumab at fixed dose. If not, permanently discontinue atezolizumab and cobimetinib.^{a, b, c} • If event resolves to Grade 1 or better within 28 days, resume cobimetinib with dose reduced by one level. If not, permanently discontinue cobimetinib.

GI = gastrointestinal; IV = intravenous; NSAID = non-steroidal anti-inflammatory drug.

^a If corticosteroids have been initiated, they must be tapered over ≥ 1 month to ≤ 10 mg/day oral prednisone or equivalent before atezolizumab can be resumed.

^b Atezolizumab may be withheld for a period of time beyond 105 days to allow for corticosteroids to be reduced to ≤ 10 mg/day oral prednisone or equivalent. The acceptable length of the extended period of time must be agreed upon by the investigator and the Medical Monitor.

^c Resumption of atezolizumab may be considered in patients who are deriving benefit and have fully recovered from the immune-related event. Patients can be rechallenged with atezolizumab only after approval has been documented by both the investigator (or an appropriate delegate) and the Medical Monitor.

Table 6 Guidelines for Management of Patients Who Experience Specific Adverse Events (Cobimetinib and Atezolizumab) (cont.)

Event	Action to Be Taken

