Table 6 Guidelines for Management of Patients Who Experience Specific Adverse Events (Cobimetinib and Atezolizumab) (cont.)

Event	Action to Be take
Pulmonary events	
General guidance	Mild-to-moderate events of pneumonitis have been reported with atezolizumab and cobimetinib. All pulmonary events should be thoroughly evaluated for other commonly reported etiologies such as pneumonia/infection, lymphangitic carcinomatosis, pulmonary embolism, heart failure, chronic obstructive pulmonary disease, or pulmonary hypertension. For events concerning for pneumonitis, consider comprehensive infectious evaluation including viral etiologies.
Pneumonitis, Grade 1 (asymptomatic)	
 • Continue atezolizumab and cobimetinib. • Re-evaluate on serial imaging. • Consider patient referral to pulmonary specialist.
Pneumonitis, Grade 2	
 • Withhold atezolizumab and cobimetinib. • Refer patient to pulmonary and infectious disease specialists and consider bronchoscopy or BAL. • If bronchoscopy is consistent with immune-related etiology, initiate treatment with 1–2 mg/kg/day oral prednisone or equivalent. • Resume atezolizumab and cobimetinib if event resolves to Grade 1 or better within 105 days.^{a, b} • Permanently discontinue atezolizumab and cobimetinib and contact Medical Monitor if event does not resolve to Grade 1 or better within 105 days.^{a, b, c} • For recurrent events, treat as a Grade 3 or 4 event.
Pneumonitis, Grade 3 or 4	
 • Permanently discontinue atezolizumab and cobimetinib.^c • Refer patient to pulmonary and infectious disease specialists and consider bronchoscopy or BAL. • If bronchoscopy is consistent with immune-related etiology, initiate treatment with 1–2 mg/kg/day oral prednisone or equivalent. • If pulmonary event does not improve within 48 hours or worsens, consider adding an immunosuppressive agent (e.g., infliximab, cyclophosphamide, IVIg, or mycophenolate). • If event resolves to Grade 1 or better, taper corticosteroids over ≥ 1 month.

BAL = bronchoscopic alveolar lavage; IVIg = intravenous immunoglobulin.

^a If corticosteroids have been initiated, they must be tapered over ≥ 1 month to ≤ 10 mg/day oral prednisone or equivalent before atezolizumab can be resumed.

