^b Atezolizumab may be withheld for a period of time beyond 105 days to allow for corticosteroids to be reduced to ≤ 10 mg/day oral prednisone or equivalent. The acceptable length of the extended period of time must be agreed upon by the investigator and the Medical Monitor.

^c Resumption of atezolizumab may be considered in patients who are deriving benefit and have fully recovered from the immune-related event. Patients can be rechallenged with atezolizumab only after approval has been documented by both the investigator (or an appropriate delegate) and the Medical Monitor.

Table 6 Guidelines for Management of Patients Who Experience Specific Adverse Events (Cobimetinib and Atezolizumab) (cont.)

Event	Action to Be Taken
Ocular toxicity	
General guidance	
 • An ophthalmologist should evaluate visual complaints. • Uveitis or episcleritis and other immune-mediated ocular disease may be associated with atezolizumab and may be treated with topical corticosteroid eye drops. Atezolizumab should be permanently discontinued for immune-related ocular event that is unresponsive to local immunosuppressive therapy. • Serous retinopathy is associated with cobimetinib. In clinical trials, most events were Grade 1 (asymptomatic) or 2 (symptomatic). Most events in clinical trials resolved or improved to asymptomatic Grade 1 following dose interruption or reduction. If serous retinopathy is diagnosed, cobimetinib should be withheld until visual symptoms improve to Grade ≤ 1. Serous retinopathy can be managed with treatment interruption, dose reduction, or treatment discontinuation. • RVO has been reported in patients treated with MEK inhibitors other than cobimetinib.

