Dyspnea, cough, fatigue, hypoxia, pneumonitis, and pulmonary infiltrates have been associated with the administration of atezolizumab. Patients will be assessed for pulmonary signs and symptoms throughout the study and will also have computed tomography (CT) scans of the chest performed at every tumor assessment.

All pulmonary events should be thoroughly evaluated for other commonly reported etiologies such as pneumonia or other infection, lymphangitic carcinomatosis, pulmonary embolism, heart failure, chronic obstructive pulmonary disease, or pulmonary hypertension. Management guidelines for pulmonary events are provided in [Table 1](#).

Appendix 8

Risks Associated with Atezolizumab and Guidelines for Management of Adverse Events Associated with Atezolizumab (cont.)

Table 1 Management Guidelines for Pulmonary Events, Including Pneumonitis

Event	Management
Pulmonary event, Grade 1	
 • Continue atezolizumab and monitor closely. • Re-evaluate on serial imaging. • Consider patient referral to pulmonary specialist.
Pulmonary event, Grade 2	
 • Withhold atezolizumab for up to 12 weeks after event onset.^a • Refer patient to pulmonary and infectious disease specialists and consider bronchoscopy or BAL. • Initiate treatment with 1–2 mg/kg/day oral prednisone or equivalent. • If event resolves to Grade 1 or better, resume atezolizumab.^b • If event does not resolve to Grade 1 or better while withholding atezolizumab, permanently discontinue atezolizumab and contact Medical Monitor.^c • For recurrent events, treat as a Grade 3 or 4 event.
Pulmonary event, Grade 3 or 4	
 • Permanently discontinue atezolizumab and contact Medical Monitor.^c • Bronchoscopy or BAL is recommended. • Initiate treatment with 1–2 mg/kg/day oral prednisone or equivalent. • If event does not improve within 48 hours after initiating corticosteroids, consider adding an immunosuppressive agent. • If event resolves to Grade 1 or better, taper corticosteroids over ≥ 1 month.

BAL = bronchoscopic alveolar lavage.

^a Atezolizumab may be withheld for a longer period of time (i.e., > 12 weeks after event onset) to allow for corticosteroids (if initiated) to be reduced to ≤ 10 mg/day oral prednisone or equivalent. The acceptable length of the extended period of time must be agreed upon by the investigator and the Medical Monitor.

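### Appendix 8 and Table 6 set different default limits on an atezolizumab hold (84 and 105 days) for several overlapping events, and nothing says which governs in Cohorts A and B

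*Combined protocol and SAP*

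**What the plan says.** Appendix 8 (Table 1, Grade 2 pulmonary event) reads "Withhold atezolizumab for up to 12 weeks after event onset", followed by "If event does not resolve to Grade 1 or better while withholding atezolizumab, permanently discontinue atezolizumab and contact Medical Monitor". The same pair of instructions appears there for Grade 2 hepatic events lasting more than 5 days, Grade 2 and Grade 3 diarrhea or colitis, Grade 3 dermatologic events and Grade 3 or 4 amylase or lipase elevation. A footnote lets the hold run past 12 weeks so that steroids can be reduced, for a period agreed between investigator and Medical Monitor. Another footnote allows re-challenge after permanent discontinuation, with documented approval from both.

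Table 6 in Section 5.1.3.3 uses a different limit. Its general guidance says "If atezolizumab is withheld for > 105 days because of toxicity, the patient should be discontinued from atezolizumab"; the sentence goes on to exempt cases where the Medical Monitor approves resumption. For Grade 2 pneumonitis it says "Resume atezolizumab and cobimetinib if event resolves to Grade 1 or better within 105 days". For Grade 2 and Grade 3 colitis it says "If event resolves to Grade 1 or better within 105 days, resume atezolizumab at fixed dose. If not, permanently discontinue atezolizumab and cobimetinib". Its own steroid footnote says "Atezolizumab may be withheld for a period of time beyond 105 days to allow for corticosteroids to be reduced", so the extension begins after 105 days rather than after 12 weeks. The re-challenge footnote is the same in substance as in Appendix 8.

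On scope, Section 4.2.2.2 points to Table 6 for events related to the combination and to Appendix 8 for atezolizumab-specific events, with no cohort named. Section 5.1.3.3 refers to Appendix 8 for atezolizumab-related events and then to Table 6. Section 5.1 says that the guidelines are separate for the three arms, but neither table is labelled by cohort.

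**The concern.** These are two stated stopping rules for the same drug and, in several rows, the same event. A site treating a Cohort A or B patient is sent to both and cannot follow both once the shorter limit has passed and the longer one has not.

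Two things are at stake. The first is consistent patient management, because the page consulted decides whether a late-resolving event ends atezolizumab or allows it to restart. The second is the safety reporting in Section 6.5, which summarizes adverse events that led to stopping or interrupting study drug, as well as exposure. If sites within Cohorts A and B follow different tables, the same clinical course can be counted differently in both summaries.

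**Working it through.** **Step 1. Put the rows side by side.**

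| Event | Appendix 8 default | Table 6 default |
|---|---|---|
| Pneumonitis, Grade 2 | Table 1: 12 weeks from onset; prednisone started | 105 days; steroids if bronchoscopy points to an immune cause |
| Diarrhea, intolerable Grade 2 or Grade 3 | Table 3: 12 weeks from onset | 105 days |
| Colitis, Grade 2 or 3 | Table 3: 12 weeks from onset | 105 days |
| Dermatologic, Grade 3 | Table 9: 12 weeks from onset, to Grade 1 | 105 days; one bullet resumes at Grade 2, the next discontinues if Grade 1 is not reached |
| AST/ALT elevation, Grade 2, suspected immune-related, more than 5 days | Table 2: 12 weeks from onset | 105 days; withholding is only to be considered |
| Amylase or lipase, Grade 3 or 4 | Table 8: 12 weeks from onset; steroids only to be considered if no improvement | Catch-all row, if treatment-related: 105 days |

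**Step 2. Convert to one unit.** 12 × 7 = 84 days. 105 / 7 = 15 weeks. Difference: 105 − 84 = 21 days. Ratio: 105 / 84 = 1.25. With dosing every 2 weeks in Cohorts A and B, 21 / 14 = 1.5 dosing intervals.

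**Step 3. Check the clock.** Appendix 8 counts from event onset. The event rows of Table 6 give no start, and its general rule counts time withheld. If both start at onset, the disputed window is Days 85 to 105. If Table 6 starts at the hold and the lag from onset to hold is 0 to 14 days (an assumed range), the upper end lies between Day 105 + 0 = 105 and Day 105 + 14 = 119.

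**Step 4. Allow for steroids.** Both tables require a taper of at least 1 month before restart. Assume 30 days, starting on the day of resolution.

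- Resolution on Day 85 gives an earliest restart on Day 85 + 30 = 115; resolution on Day 105 gives Day 135. Both are past either limit, so restart depends on an agreed extension under either table.
- Resolution on Day 54 gives Day 84, and resolution on Day 75 gives Day 105. For resolution on Days 55 to 75, the hold therefore ends past the Appendix 8 limit but within the Table 6 limit. An agreed extension is needed under one table and not under the other.

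**Step 5. Find a case where the steroid footnote does not apply.** Steroids are optional for Grade 3 or 4 amylase or lipase elevation in Appendix 8, and conditional for Grade 2 pneumonitis in Table 6. Where none are given, the extension is unavailable and the 84-day and 105-day defaults meet directly. Section 1.3.5.1.1 reports Grade ≥ 3 amylase increase and Grade ≥ 3 lipase increase at 5.0% each among the melanoma patients of the earlier combination study, so the case is not far-fetched. Those figures are event rates; they do not say how long the events lasted.

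**Step 6. Look for a tie-break.** Sections 4.2.2.2, 5.1 and 5.1.3.3 give none. Section 4.5.3 refers treatment discontinuation to Appendix 7, which covers anaphylaxis precautions only.

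**The case against.** The best defence is that neither limit is hard. Appendix 8 calls for steroids in most of the affected rows, so a patient still above Grade 1 at Day 84 will often be one for whom the taper extension can be agreed. Re-challenge remains possible after permanent discontinuation, and the Table 6 general rule yields to Medical Monitor approval. This stands, and it narrows the conflict to the default rules. It does not remove it. The extension exists to bring steroids down, not to wait for the event to resolve, and it starts at a different time in each table. Re-challenge requires full recovery, patient benefit and two documented approvals, whereas the ordinary Table 6 restart asks for Grade 1 or better in time.

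A second defence is that Section 5.1, the title of Table 6, and its explicit deferrals to Appendix 8 for infusion reactions and immune-related ocular events together imply that Table 6 governs Cohorts A and B for everything else. That is a plausible reading, but no text states it, and Section 5.1.3.3 refers to Appendix 8 for atezolizumab-related events generally.

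A reader might also infer more than the documents support:

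- **That Appendix 8 applies 12 weeks throughout.** It does not. Symptomatic thyroid disorders, Grade 3 or 4 hyperglycemia and possible systemic immune activation are withheld without that limit.
- **That all overlapping events conflict in this way.** For Grade 3 hepatic events Appendix 8 discontinues at once, which is a different conflict. Tolerable Grade 2 diarrhea continues under Table 6. Immune-related ocular events follow Appendix 8 under both.
- **That discontinuation rates in Cohort C and Cohorts A and B are made non-comparable by this.** Section 6 summarizes Cohort C separately, Section 6.1 plans no formal testing, and the cohorts already differ in drugs, prior therapy and cycle length.

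**Conclusion.** The two tables contradict each other on the default maximum hold for the events listed in the working: 84 days from onset against 105 days, a gap of 21 days. The conflict reaches Cohorts A and B because the protocol directs them to both tables without a rule of precedence.

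Opposite outcomes follow for an event that resolves after Day 84 and by Day 105, on two conditions: both clocks start at onset, and no taper extension, re-challenge or Medical Monitor approval is in place. It would be wrong to conclude that every patient resolving in that window is classified in opposite ways, since any of those three routes can bring the outcomes together. With a different clock start, the window moves as shown in Step 3.

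The number of patients affected cannot be estimated from the documents; the 1.25 ratio describes the rules and not their effect. Sample size, confidence intervals and the ORR and DCR definitions are unaffected. The point is worth correcting because it bears on a treatment-stopping decision and on the planned discontinuation and exposure summaries.

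**What to change.** Reconcile Table 6 and Appendix 8 on three items: the maximum hold, the event from which it is counted, and the cohorts or events to which each table applies. Alternatively, keep both limits and state which table governs in Cohorts A and B. The sponsor chooses the values; this review takes no view on which limit is right. While the text is open, align the point at which the steroid-taper extension begins, and have Section 4.5.3 refer to the governing table. The cost is a wording change in the protocol and a clarification to sites. No analysis or sample-size change follows.
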